11 EXTENT OF EXPOSURE TO STUDY DRUG

Exposure will be summarized using descriptive statistics such as n, mean, standard deviation, median, minimum, and maximum for the following variables:

- Average of daily doses (mg/day) received
- Average of dosing frequency (day) per week
- Total amount of study drug (mg) received
- Total duration of treatment in number of months, calculated by last dosing day minus first dosing day add 1 then divided by 30.
- Number of patients who had duration in different categories: less than 12 months, between 12 months and 24 months, between 24 months and 36 months, between 36 months and 48 months, longer than 48 months.
- Number of patients which had average daily dose in different categories: <20 mg/day, ≥20 mg/day to <40 mg/day, ≥40 mg/day to <60 mg/day, ≥60 mg/day.

When calculating the total exposure duration on study drug, any dose interruption longer than 28 days will be excluded from the calculation.

	SAP PAL-003 Amendment 1 version 1.0	Page 21
---	-------------------------------------	---------

12 EFFICACY EVALUATIONS

Efficacy measurement (blood Phe concentration) from start of parent studies (PAL-002, PAL-004, 165-205) to 14 days after last dose of pegvaliase will be summarized using descriptive statistics for the CSR for PAL-003. Baseline blood Phe concentration is defined as the last available measurement prior to first administration of study drug from parent studies (PAL-002, PAL-004, 165-205). All efficacy data collected 14 days after the last dose in the study will not be included in the analysis.

As the measure of efficacy, observed blood Phe concentration at scheduled time point, change from baseline and percentage change from baseline in blood Phe concentration at scheduled time point, daily dose at which subject first had blood Phe values $\leq 600 \text{ } \mu\text{mol/L}$, daily dose at which subject first had blood Phe values $\leq 360 \text{ } \mu\text{mol/L}$, daily dose at which subject first had at least 20% blood Phe reduction from baseline using the average of 2 consecutive blood Phe assessments, time to when subject first had blood Phe values $\leq 600 \text{ } \mu\text{mol/L}$, time to when subject first had blood Phe values $\leq 360 \text{ } \mu\text{mol/L}$, and time to when subject first had two consecutive Phe values with at least 20% blood Phe reduction will be summarized using descriptive statistics for the efficacy population. Percent of subjects with blood Phe concentration $\leq 360 \text{ } \mu\text{mol/L}$ and percent of subjects with blood Phe concentration $\leq 600 \text{ } \mu\text{mol/L}$ over time will also be summarized and plotted.

To investigate the primary objective, last observation carry forward (LOCF) imputation approach will be used as sensitivity analyses.

The distribution of responses in blood Phe concentration will be evaluated using the cumulative distribution function (CDF) (McLeod 2011). The percentage of subjects responding at the beginning of PAL-003, the end of first year of PAL-003 and the end of PAL-003 will be plotted against the continuous range of responses. Thus, the CDF will show a continuous plot of the proportion of subjects at each time point along the continuum of Phe levels, an approach that offers a visual comparison of the separation among the three timepoints across all levels of change so that a variety of responder definitions can be considered simultaneously. In a rare disease setting, such as with PKU, this approach is proposed over applying a categorical responder definition due to the limitations in sample size.

A subject listing of blood Phe concentration will be provided. A summary table will be provided on the percent of subjects in each quartile of blood Phe concentration at each scheduled time point. Plots for mean blood Phe concentration, change from baseline and

	SAP PAL-003 Amendment 1 version 1.0	Page 22
---	-------------------------------------	---------

percentage change from baseline in blood Phe concentration will also be generated for both observed values and values after LOCF imputation.

For the diet diary, standard descriptive statistics will be presented for the observed, change from baseline and percent change from baseline values of the three-day average of dietary protein, tyrosine and dietary phenylalanine at each visit. The three-day average diet diary results will also be listed. To explore the change in blood Phe concentration with respect to changes in subject diet, plots will be generated for mean blood Phe concentration with mean dietary protein and mean dietary Phe, mean change from baseline blood Phe concentration with mean change from baseline of dietary protein and dietary Phe.

	SAP PAL-003 Amendment 1 version 1.0	Page 23
---	-------------------------------------	---------

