4 GENERAL ANALYSIS CONSIDERATION

Descriptive summaries of continuous variables will include the number of subjects (n), mean, standard deviation, median, minimum, and maximum. Descriptive summaries of categorical variables will include n and percent. Data from parent studies (PAL-002, PAL-004, 165-205) will be integrated together with data in PAL-003 for long term safety and efficacy analysis. The baseline value of an assessment is defined as the last available measurement prior to first administration of study drug from parent studies (PAL-002, PAL-004, 165-205), unless otherwise specified.

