4.1 Analysis Populations

4.1.1 Efficacy

The efficacy population will consist of all subjects who receive at least one dose of study drug and have post-treatment blood Phe concentration measurements in any of the phase 2 studies (PAL-002, PAL-004, 165-205, PAL-003).

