4.6 Handling of Dropouts and Missing Data

Subjects who discontinued prematurely will not be replaced. To investigate the primary objective, last observation carry forward (LOCF) imputation approach will be used as sensitivity analyses.

	SAP PAL-003 Amendment 1 version 1.0	Page 13
---	-------------------------------------	---------

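### Times to first blood Phe response get plain descriptive statistics, with no censoring and no rule for subjects who never reach the level or stop first

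*SAP*

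**What the plan says.** Section 12 names three times to first response among the efficacy measures: time to first blood Phe ≤600 µmol/L, time to first blood Phe ≤360 µmol/L, and time to the first pair of successive results "with at least 20% blood Phe reduction will be summarized using descriptive statistics for the efficacy population". Section 12 also summarises the daily dose at which each of the three responses first occurred.

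Section 4 fixes what a descriptive summary is: "Descriptive summaries of continuous variables will include the number of subjects (n), mean, standard deviation, median, minimum, and maximum".

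Section 4.1.1 defines the population without reference to response: "The efficacy population will consist of all subjects who receive at least one dose of study drug and have post-treatment blood Phe concentration measurements". This takes in the parent studies as well as PAL-003.

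On incomplete follow-up, Section 4.6 says "Subjects who discontinued prematurely will not be replaced" and offers LOCF as a sensitivity analysis for the primary objective. Section 12 limits efficacy data to 14 days after the last dose. It also plans the percentage of subjects at ≤360 and ≤600, which "over time will also be summarized and plotted". The readable text contains no censoring rule, survival estimate or assigned time for a subject without the event.

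**The concern.** A time to first response exists only for a subject who responds while observed. Everyone else in the efficacy population has at most a lower bound: no response up to the last Phe assessment. A mean or median of complete values cannot use that information, so whoever programs the table must choose. Leaving these subjects out is the natural reading. Entering the stopping time as if it were the response time is the other obvious choice. Both comply with the SAP, and they give different answers.

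Incomplete observation is to be expected. Section 11 tabulates treatment duration from under 12 to over 48 months, Table 1 runs to Week 416, and Section 6 summarises premature discontinuation.

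At stake is how the result is read. A median time to response shown for the efficacy population will be taken as the time a treated subject needs to reach the level. On the natural reading it describes only those who reached it while under observation, and it would look much the same whether most or only some subjects responded.

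**Working it through.** The SAP states no sample size, response rate or dropout rate (Section 3.5 says no formal calculation was made). There is no figure to reproduce, and every input below is an assumption.

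**Does the text supply an event time?**

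| Provision | Does it settle subjects without the event? |
|---|---|
| Section 4, descriptive statistics | No. It needs a complete value for each subject counted. |
| Section 4.1.1, efficacy population | No. Non-responders are included. |
| Section 4.6 and Section 12, LOCF | No. It carries a concentration forward and creates no time. |
| Section 12, 14-day limit | No. It restricts the data used and is not stated as a censoring date. |
| Section 12, percentages over time | No. They are status at each visit, not cumulative first attainment, and the 20% reduction is not covered. |

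**Illustration A: censoring alone, everyone eventually responds.** Time to response is exponential with rate λ = ln 2 / m, where m is the true median. Dropout is exponential with rate δ = −ln(1 − d)/52 per week, where d is the annual dropout proportion. Follow-up ends at F weeks. Put s = λ + δ and q = 1 − exp(−sF). Then:

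- share observed to respond = (λ/s)·q
- responder-only median = −ln(1 − q/2)/s
- median with the stopping time entered as the event = ln 2 / s (when this is below F)

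Take m = 52, d = 0.20 and F = 104. Then λ = 0.01333, δ = 0.00429, s = 0.01762 and q = 1 − exp(−1.8326) = 0.84.

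- Share responding: (0.01333/0.01762) × 0.84 = 0.64.
- Responder-only median: −ln(0.58)/0.01762 = 30.9 weeks (30.8 by simulation of 1,000,000 subjects).
- Stopping time as event: 0.6931/0.01762 = 39.3 weeks.

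Both stand against a true 52 weeks. Simulated ranges over d = 10%, 20% and 30% and F = 104 and 208 weeks:

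| True median (weeks) | Responder-only median | Stopping time as event |
|---|---|---|
| 26 | 19.8–24.1 | 20.7–24.2 |
| 52 | 28.5–42.4 | 34.3–45.1 |
| 104 | 35.0–62.1 | 51.3–79.9 |

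The responder-only median is 7% too early at best (24.1 against 26) and 66% at worst (35.0 against 104). Between 37% and 93% of subjects are observed to respond.

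**Illustration B: longer follow-up, and some subjects never respond.** There are 80 subjects. Time is lognormal with median 12 months in those able to respond, with log-SD σ of 0.5, 0.8 or 1.0. Follow-up is uniform on 3–84 months. Each scenario has 4000 simulated trials. When a fraction p can respond, the true all-subject median is 12·exp(σ·Φ⁻¹(0.5/p)). For p = 0.6 and σ = 0.8 this is 12·exp(0.8 × 0.967) = 26.0 months, close to the simulated Kaplan-Meier median.

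| Able to respond | Responder-only median (months) | Kaplan-Meier median (months) | n in the responder-only table, of 80 |
|---|---|---|---|
| 100% | 11.5, 10.6, 9.8 (by σ) | about 12.0 | about 65–70 |
| 90% | 9.8–11.5 | 12.8–13.8 | about 58–63 |
| 75% | 9.8–11.5 | 14.9–18.5 | about 48–52 |
| 60% | 9.8–11.5 | 19.5–31.9, not reached in 5–13% of trials | about 39–42 |

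The first row is pure censoring bias: 0.5/12 = 4%, 1.4/12 = 12% and 2.2/12 = 18% too early. In the 75% and 60% rows most of the gap is a difference of estimand (all subjects against responders), not bias.

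Sensitivity at σ = 0.8: with 40 or 120 subjects the medians were essentially unchanged. With follow-up of 3–48 or 12–84 months the responder-only median was 9.5–9.6 or 11.0–11.1 months.

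**The case against.** The strongest reply is that this is an open-label, descriptive extension whose other outputs already show who responds. If only responders are summarised, the table's n divided by the efficacy population count (Section 5) gives crude ever-attainment for all three events. Section 12 adds by-visit percentages, a quartile table, a listing of Phe values and cumulative distribution plots, and it prefers those plots to a categorical responder definition. The SAP does not actually say non-responders are dropped. Time to response among responders is a legitimate description if labelled, and a dose at first response can exist only for responders.

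Part of this stands. The defect is an unfixed rule rather than an explicitly chosen responder-only estimator. The dose point is a matter of labelling. The size cannot be fixed from the SAP: Illustration A stops at 208 weeks while Table 1 runs to Week 416, and longer follow-up shrinks the bias.

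Kaplan-Meier also has its own assumption. Only subjects who completed a parent study enter PAL-003, yet the efficacy population takes in treated parent-study subjects with Phe data. If stopping, or not rolling over, goes with poor response, censoring is informative and the estimate is biased too.

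None of this rescues the stated summary. The n does not separate never responding from stopping early and does not correct the median. The other outputs give no time to response. Informative dropout limits how Kaplan-Meier is read, but it does not favour a method that discards or misdates the same subjects.

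**Conclusion.** The concern holds and should be fixed. Section 12 assigns three event times to a method that requires complete values, in a population that need not have them, and no other section closes the gap. Either obvious way of completing the table can bias the median early.

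The size is illustrative only. It runs from 4% to 18% with a 12-month median and follow-up to 84 months, and from 7% to 66% under exponential response with follow-up of 104 or 208 weeks. Both ranges assume censoring independent of response. The more robust result is qualitative: under the assumptions of Illustration B the responder-only median stays at 9.8–11.5 months whether all subjects or only 60% can respond.

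The harm is confined to the secondary descriptions of how soon treatment works. Phe concentration and change from baseline, which serve the primary objective, are not affected.

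**What to change.** In Section 12, for the three time-to-first-response variables:

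- Use Kaplan-Meier estimates from first dose in the full efficacy population.
- Censor subjects without the event at their last Phe assessment within the efficacy window (to 14 days after last dose).
- Report the median with 95% CI, or state that it was not reached. Add the cumulative percentage responding at fixed times, for example 6, 12, 24 and 36 months.
- Report the number never reaching each level, and note that the estimate assumes stopping is unrelated to response.
- Label the dose-at-first-response summaries as being among responders, with the number never reaching the level beside each.

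If a responder-only time summary is kept as well, label it the same way.

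The cost is SAP wording and a few standard tables or figures, with no new data. Reported medians will be longer or may not be reached. In that case the cumulative percentages should carry the result.

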13 PHARMACOKINETIC EVALUATIONS

A subject listing of plasma pegvaliase concentration and a listing of PK parameters will be provided. Scatter plots of dose-normalized trough plasma pegvaliase concentration at the last visit of PAL-003 vs. antibody measurements will also be provided. The PK analysis plan will be detailed in a separate document.

	SAP PAL-003 Amendment 1 version 1.0	Page 24
---	-------------------------------------	---------

14 SAFETY EVALUATIONS

Safety will be assessed by examining the incidence, exposure adjusted event rate, severity grade, and relationship to study drug of all treatment-emergent adverse events (TEAEs) reported during the study period. In addition, changes in clinical laboratory results and vital signs from baseline values from parent studies (PAL-002, PAL-004, 165-205) will be assessed. All safety data collected 30 days after the last dose will not be included in the analysis.

AEs will be coded in accordance with the MedDRA version 18.0. Only treatment-emergent adverse events (TEAEs) occurring and reported during the study period will be included in the adverse event summaries. A TEAE is defined as any AE that newly appeared or worsened in severity following initiation of the study drug administration till 30 days after last dose of the phase 2 studies (PAL-002, PAL-004, 165-205, PAL-003). If the onset date of an AE is missing, the AE will be considered treatment-emergent.

If the onset date or end date of an adverse event is partial, the same imputation rules described in section 10 will be applied:

The incidence and frequency of all treatment-emergent AEs will be summarized by SOC, preferred term (PT), and severity grade. For those AEs that occurred more than once during the study, the maximum severity will be used to summarize the AEs by severity. The SOCs and PTs will be displayed by descending order based on total population.

The treatment-emergent AEs will be summarized in the following categories:

- All AEs by SOC and preferred term
- All AEs by SOC, preferred term, and severity
- AEs assessed by the investigator as related to study drug by SOC and preferred term
- AEs assessed by the investigator as related by SOC, preferred term and severity
- Serious AEs (SAEs) by SOC and preferred term
- SAEs assessed by the investigator as possibly or probably related to study drug by SOC and preferred term
- All AEs by preferred term in descending frequency order
- Hypersensitivity AE by SOC and PT
- Hypersensitivity AE by SOC, PT and severity
- Neuropsychiatric AE by SOC, PT and severity

	SAP PAL-003 Amendment 1 version 1.0	Page 25
---	-------------------------------------	---------

AE assessed by investigators as related to PFS/Device malfunction

- AEs leading to dose interruption or reduction by SOC and preferred term
- AEs leading to withdrawal from study by SOC and preferred term
- AEs leading to study drug discontinuation by SOC and preferred term
- Pregnancy
- Death

In addition to the standard summary tables and listings, the following information will also be summarized for AEs of special interest, and sponsor defined AEs of significance:

- Time to event onset from most recent dose for Anaphylaxis per NIAID/FAAN criteria and Anaphylaxis per NIAID/FAAN criteria meeting Brown's severe criteria
- Time to first event onset per subject from first dose
- Duration of the events
- Patient characteristics for subjects with special types of hypersensitivity AEs except for injection site reaction and arthralgia
- Actions related to study drug
- Common treatment
- Incidence rate over time

The AEs of special interest include:

- Anaphylaxis per NIAID/FAAN criteria
- Anaphylaxis per NIAID/FAAN criteria meeting Brown's severe criteria

The sponsor defined AEs of significance include:

- Hypersensitivity AEs
- Injection site reaction
- Generalized skin reaction with ≥ 14 day duration
- Injection site skin reaction with ≥ 14 day duration
- Arthralgia

The search strategy for AEs of special interest and sponsor defined AEs of significance is in [Appendix 1](#).

In addition to standard AE listings, by subject listings of injection site reaction AEs, AEs of special interest, sponsor defined AEs of significance, and psychiatric AEs under each

BIOMARIN	SAP PAL-003 Amendment 1 version 1.0	Page 26
-----------------	-------------------------------------	---------

identification strategies will be provided. Study drug dose level at onset date of each of the AE will be presented on the listings. AEs will be sorted by onset date, preferred term, and dose of study drug at event onset date. Number of Hypersensitivity AE will be plotted over time (1-6 month, 6-12 month, and once each year after).

Death information will also be displayed in a listing.

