10 PRIOR AND CONCOMITANT MEDICATIONS/PROCEDURES

Prior and concomitant medications taken prior to, on or after the first dose of pegvaliase will be summarized for all enrolled subjects. For analysis purposes, the following definitions will be used to determine prior and concomitant medications:

- Prior medications: any medications taken within 30 days prior to the screening and prior to the initial pegvaliase administration date
- Concomitant medications: any medications initially taken on or after the initial pegvaliase administration date
- Prior and concomitant medications: any medications taken both prior to the initial pegvaliase administration date and on or after the initial pegvaliase administration date will be reported both as prior and concomitant medications. Therefore, any medications taken prior to the pegvaliase first dose date where the stop date is reported as “continuing” will be considered both as prior and concomitant medications.

In the event the start date of a medication is completely missing, the start date will be imputed as the first dose date if the stop date is in the same year or later than the first dose date.

In the event the start date of a medication is partial, the following imputation rules will be applied:

- If only day is missing, then the start date will be imputed as the first day of the month, if the year and month is after the first dose year and month. If only day is missing, then the start date will be imputed as the last day of the month, if the year and month is prior to the first dose year and month. If month is the same as the month of first dose of pegvaliase then the start date will be imputed as the first dose date of pegvaliase.
- If only year is non-missing, then the start date will be imputed as the first day of the year if the year is after the year of first dose. If year is the same as the year of first dose of pegvaliase then the start date will be imputed as the first dose date of pegvaliase. If year is before the year of first dose of study drug then the start date will be imputed to the first day of July of the year.

In the event the stop date of a medication is partial, the following imputation rules will be applied:

- If only day is missing, then the end date will be imputed as the last day of the month.
- If only year is non-missing, then the end date will be imputed as the last day of the year.

	SAP PAL-003 Amendment 1 version 1.0	Page 19

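### SAP section 14 applies the medication-date imputation to partial AE dates, which can lengthen AE duration and move short skin reactions into the ≥ 14-day classes; the overall size is unknown and may be small

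*SAP*

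**What the plan says.** SAP section 14 borrows the date rules that section 10 sets out for prior and concomitant medications: "If the onset date or end date of an adverse event is partial, the same imputation rules described in section 10 will be applied".

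In section 10 the end-date rules are "If only day is missing, then the end date will be imputed as the last day of the month" and "If only year is non-missing, then the end date will be imputed as the last day of the year". For onset, section 10 says "If only day is missing, then the start date will be imputed as the first day of the month", on condition that the month is later than that of the first dose. If the month is that of the first dose, the start becomes the first-dose date.

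Section 14 then uses AE length in two ways:
- It summarises "Duration of the events" for AEs of special interest and sponsor-defined AEs of significance.
- Two of the five sponsor-defined AEs of significance carry a length criterion: "Generalized skin reaction with ≥ 14 day duration" and "Injection site skin reaction with ≥ 14 day duration".

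For how the classes are identified, section 14 refers elsewhere: "The search strategy for AEs of special interest and sponsor defined AEs of significance is in" Appendix 1. The content of that appendix is not shown in the copy reviewed.

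The visible text makes no exception for duration-based outputs, sets no upper limit on an imputed AE end date, and plans no summary restricted to complete dates.

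**The concern.** The section 10 rules serve a yes/no question: was a medication in use on or after the first dose? For that purpose a late stop date is a harmless default. An AE's length is a measurement, and a default at the latest possible end is biased for it. The end-date rule can leave duration unchanged or lengthen it, and can never shorten it. After the first-dose month the onset rule pulls the other end of the interval earlier, which adds to the error.

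Two outputs are at stake. One is the duration summary, where a few year-end imputations can dominate the mean and the maximum. The other is the count in the two prolonged skin-reaction classes, where an event may enter because its dates are incomplete and not because it lasted two weeks.

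**Working it through.** The SAP gives no figure on this point, so there is none to reproduce. The check applies the stated rules to every onset day of a 365-day year.

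**Inputs.** The imputation rules are from section 10 and the 14-day threshold from section 14. Two inputs are assumed. Duration is end − onset + 1, because the SAP gives no formula for AE duration. True durations k are below 14 days, with onset spread evenly over the year.

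**1. Onset known, only the end day missing.** If the true end falls on day j of a month with M days, the imputed duration is k + (M − j). It stays below 14 only when M − j ≤ 13 − k, which is 14 − k end days in each month. So the share reaching 14 days is 1 − 12 × (14 − k)/365.

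| True duration | Calculation | Share reaching ≥ 14 days | Without the +1 |
|---|---|---|---|
| 3 days | 1 − 132/365 | 63.8% | 1 − 144/365 = 60.5% |
| 7 days | 1 − 84/365 | 77.0% | 1 − 96/365 = 73.7% |

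The mean number of added days is the average of M − j over the year: (7 × 465 + 4 × 435 + 378)/365 = 5373/365 = 14.7. For example, onset 5 March with end recorded as March gives 31 − 5 + 1 = 27 days, whatever the true length.

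**2. Onset known, end known only to the year.** The share is 1 − (14 − k)/365, which is 97.0% for 3 days and 98.1% for 7 days, with 182 days added on average. The 5 March example becomes 302 days. Nothing in the SAP indicates that year-only end dates occur for skin reactions, so this is an extreme case.

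**3. Onset day and end day both missing, after the first-dose month.** The imputed interval covers at least one whole month, hence at least 28 days. All such events reach the threshold, and the mean addition is 2 × 14.7 = 29.4 days.

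**4. Both days missing, in the first-dose month.** Onset becomes the first-dose date, so the result varies. With a first dose on 20 March and both AE dates recorded as March, the imputed duration is 31 − 20 + 1 = 12 days, below the threshold. With a first dose on 5 March it is 27 days.

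**5. Effect over all 3-day reactions.** The SAP does not give the share q with a missing end day. The misclassified share is q × 63.8% and the rise in mean duration is q × 14.7 days.

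| q | Misclassified | Added to mean duration |
|---|---|---|
| 1% | 0.6% | 0.15 days |
| 5% | 3.2% | 0.74 days |
| 10% | 6.4% | 1.5 days |

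**The case against.** The strongest objection is that the classes are defined in Appendix 1, which is not shown and could contain its own rule for the 14-day criterion. This stands as a limit on the part about the two classes. It does not touch the duration summary, which section 14 sets out directly.

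Second, the percentages in steps 1 to 3 are conditional on incomplete dates. A reader might infer that most short skin reactions will be misclassified. The SAP does not support that, because it gives no information on how often AE dates are partial. If few are, the bias is small.

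Three further readings go too far:
- That any event with both days missing in one month must qualify. Step 4 shows this fails in the first-dose month.
- That duration alone defines the two classes. Each also requires a type of skin reaction.
- That partial dates come from poor recall during home dosing. The SAP mentions self-administration but says nothing on how AE dates were collected or how complete they are.

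Third, this is an open-label, descriptive extension, and over-counting prolonged reactions does not flatter the drug. By-subject listings of these AEs are also planned. That lowers the stakes, but it does not make a duration mean or a class count accurate, and the SAP does not say that imputed dates will be flagged.

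Fourth, counting only certain cases could drop truly prolonged reactions. That would be a fair criticism of a complete-dates-only rule. It is met by reporting the undetermined events beside each class.

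**Conclusion.** The point holds in a limited form. Section 14 states a rule which, followed as written, overstates the length of many AEs with a partial end date. As far as the visible text shows, it also moves some short skin reactions into the two ≥ 14-day classes. Among reactions with only the end day missing, 64% of 3-day and 77% of 7-day events cross the threshold (61% and 74% if duration is computed without the +1). With both days missing after the first-dose month, all do.

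The effect on the reported tables cannot be fixed from the SAP. It depends on the share of partial dates and on the ratio of short to prolonged reactions, and neither is given. Across shares of 1% to 10%, about 0.6% to 6.4% of 3-day reactions would be misclassified. The end-date rule errs only towards over-counting, while onsets set to the first-dose date can err either way. The conclusion rests on even spread of onsets, the assumed duration formula, and the absence of an overriding rule in Appendix 1.

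The amendment is worth making because it is cheap and removes a known bias, not because a large distortion has been shown.

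**What to change.** In SAP section 14:
- Limit the section 10 imputation for AEs to deciding treatment emergence.
- State the AE duration formula, and summarise duration from events with complete dates, giving the number excluded.
- Count an event in a ≥ 14-day class only if the shortest duration compatible with its recorded dates is at least 14 days. For example, onset 5 March with end recorded as April lasts at least 28 days and counts; onset 5 March with end recorded as March could be 1 to 27 days and does not.
- Beside each class, report as 'duration unknown' the events that could be, but are not certainly, ≥ 14 days, so that the lower and upper counts are both visible.
- Cap any imputed end date at last contact or data cut.
- Check that Appendix 1 agrees with these rules.

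Under the shortest-duration rule no reaction with a true length of 1 to 13 days can be counted as ≥ 14 days. The cost is a few sentences and a small change to the derivation code. The downside is that some events have no single duration and the certain ≥ 14-day count may be lower, which the 'duration unknown' count offsets.
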